6. STATISTICAL METHODOLOGY

6.1 Statistical and Analytical Issues

6.1.1 Statistical Methods

Descriptive statistics summary results will be produced and presented for all the data collected on the different assessments that include demographics, baseline characteristics, concomitant medications, efficacy, and safety endpoints. Continuous data summary descriptive statistics will

include the number of observations, means, standard deviations, medians, and ranges. Categorical variables will be summarized with frequencies and percentages.

The primary hypothesis testing will be two-sided statistical significance testing (alpha level = 0.05) comparing active treatment to placebo and mainly dedicated to assessing the primary endpoint and the key secondary endpoints. Point and interval estimates (95% confidence intervals) will be calculated and presented by treatment group for each parameter. Computed p-values will be rounded to four decimal places; p-values less than 0.0001 will be presented as '< 0.0001' and p-values greater than 0.9999 will be presented as '> 0.9999' in the tables.

All statistical analyses will be performed using SAS statistical software (Version 9.3 or an updated latest higher version available at the time of analysis). Adverse events will be coded using the most recent MedDRA version available at the time of analysis and the version used will be footnoted in the respective summary tables. Concomitant medications will be coded using the most recent version of World Health Organization (WHO) Drug dictionary.

6.1.2 Multiplicity and Testing Strategy

Multiplicity issues in statistical inference in this study may arise from repeated tests on several multiple endpoints specified in the protocol. Additionally, the impact of the Type I error probability (α) because of the formal planned interim analysis to be conducted needs to be understood.

The protocol specified α -spending for the planned interim analysis is 0.003. Hypotheses tests at the final analysis will be conducted at significance level of $\alpha = 0.049$. The multiple efficacy tests for the study final analysis will employ a serial sequential gatekeeper strategy to maintain the Type 1 error rate at $\alpha = 0.049$ across two families of analyses that support the primary, and key secondary objectives. The protocol pre-specified strategy is to use a hierarchy of significance tests where each test acts as a gatekeeper to tests below it. The endpoints will be tested in a sequential manner and will follow the sequential order given below starting with Remission ranked 1. Any inferential and hypothesis testing of a subsequent endpoint will be performed only if the test for the preceding endpoint is significant. In other words, the endpoint hypothesis examined earlier serves as gatekeeper. For this study as listed below in sequence of clinical importance, Remission week 26 is first rank (1) and will be tested first followed by Response week 26 (rank 2), followed by Remission week 52 (rank 3), Durable Remission week 26 through week 52 (rank 4), followed by Remission week 16 (rank 5), and followed by Steroid free Remission week 52 (rank 6). Again it is important to note that once one hypothesis is tested and found not to be significant at $\alpha = 0.049$, all subsequent tests will not be performed. The multiplicity adjustment following hierarchal testing procedure comparing RHB-104 with Placebo will only be performed on the following key clinical efficacy endpoints listed in order of clinical importance:

1. Remission (CDAI score < 150) week 26 - Primary Efficacy Endpoint.
Key Secondary Efficacy Endpoints:
2. Response (reduction from baseline of ≥ 100 in CDAI score) week 26.
3. Remission (CDAI score < 150) week 52
4. Durable Remission (CDAI score < 150) from week 26 through week 52 in remission.

5. Remission (CDAI score < 150) week 16
6. Proportion of subjects in steroid free remission week 52 (CDAI score < 150 and no steroids use by week 49).

For the endpoints not included in the above pre-specified multiple testing, the P-values and confidence intervals will be presented with NO adjustment for multiplicity. Nominal P-values and confidence intervals are consequently supplementary/supportive to the primary efficacy analyses.

6.1.3 Subgroups

To further assess consistence of the study outcome data, the primary efficacy, key secondary efficacy, and select safety data may be further broken down and summarized by the following baseline subgroups characteristics with potential differing influence on outcome:

- Sex: male, female
- Race: White, Black, Other
- Region: Countries will be grouped into geographical regions, e.g., US, Canada, Europe, etc.
- Alcohol consumption: (Yes/No)
- Smoking: (previous smoker, currently smoking, Nonsmoker)
- Prior CD treatments (e.g., surgery/no surgery)
- Years of CD (Categories to be determined at the time of analysis)
- Prior use of anti-TNF agents (yes or no)
- Prior use of immunomodulators (yes or no)
- Prior use of Corticosteroids (yes/no)
- CRP level at baseline
- Fecal Calprotectin level at baseline

The final subgroups to be assessed will be completed at the time of analysis depending on the available data by each subgroup.

6.1.4 Baseline Definition

Baseline period consists of 42 days (covering screening period) immediately preceding first administration of study treatment. Any assessment performed during these 42 days before first administration of study treatment will be considered baseline assessment. Study day 1 will be the first day of study drug administration. For all endpoints requiring baseline results, e.g., comparison with post-baseline, the baseline is the last non-missing result prior to first dose.

6.1.5 Missing Data and Handling of Dropouts

All available efficacy and safety data will be included in data listings and tabulations. All patients who prematurely discontinue for any reason will be considered failures for the different proportion based endpoints.

CDAI Missing Data:

Final Version 3.0, 05 April 2018

The computation of CDAI requires 7 days of consecutive diary daily data. For subjects with CDAI diary data reported that is less than 7 days of data, the reported data will be standardized to 7 days by dividing the sum of CDAI score over the number of days of data by total number of days of reported data multiplied by 7. If less than 4 days of diary data is available, the subject will be categorized as a non-responder and the CDAI score will be considered missing. As specified in the protocol, subjects with missing week 26 assessment will be assumed to not be in a state of remission at week 26 (i.e., non-responders). Similarly, for subjects with missing week 52 assessments will be assumed not to be in state of remission at week 52. Sensitivity analyses may be performed on Observed Case (completer analysis) only.

Handling of missing date information for AEs:

The term *missing date* refers to a completely missing date or to partial date where month or/and day or/and year is/are missing, e.g. missing month/day/year. Missing start and end dates will be imputed conservatively, i.e. missing values will be imputed in such a way that the duration of the AE is considered with the longest possible duration. The missing start date and end date of AE will be imputed for the purpose of defining treatment emergent adverse events (TEAE) and for assigning events to treatment periods using the following definitions:

(i) Adverse Event Start Date:

Event Missing Day: If Adverse event day is missing but month and year present, then impute the 1st of the month unless month and year are the same as first dose of study drug then impute day first day of dose.

Event Missing day and month – If adverse event day and month both are missing but year is present then impute 1st January unless year is the same as first dose date then impute day and month first dose day and month.

Completely missing – impute first dose date unless the end date suggests it could have started prior to this in which case impute the 1st January of the same year as the end date.

(ii) Adverse Event End Date:

Missing day – If AE day is missing but month and year is present then impute the last day of the month.

Missing day and month – If AE has missing day and month but year is present then impute 31st December.

Completely Missing – Required to look at whether the AE is still ongoing before imputing a date and also when it started in relation to study drug. If the ongoing flag is missing then assume that AE is still present (i.e. do not impute a date). If the AE has stopped and start date is prior to first dose date then impute the 1st dose date, if it started on or after first dose date then impute a date that is after the last dose date.

(iii) TEAE definition with missing start and stop dates: If the start date of an adverse event is incomplete or missing, the event will be assumed to be a treatment-emergent adverse event (TEAE), unless the incomplete start date (month and/or year) or the stop date (complete or incomplete) clearly indicates that the event started prior to dosing. Missing/incomplete information will be reported as missing/incomplete in the subject listings.

(iv) Adverse event relationship: If the relationship for an adverse event is not recorded, it will be assumed to be treatment related in the presentation of the statistical summary of incidence results. Missing information will be reported as missing in the subject listings.

(v) Adverse event severity: If the severity of an adverse event is missing, the severity will be assumed to be severe when summarizing data. Missing information will be reported as missing in the subject listings.

(vi) Non-study medication (concomitant medications, steroids) start and stop dates: If the start and/or stop dates of non-study medication use are incomplete or missing, the use will be assumed to be concomitant, unless the incomplete date information clearly indicates that the use stopped prior to study medication dosing. Missing/incomplete information will be reported as missing/incomplete in the subject listings.

6.1.6 Conversion of time interval

In case time interval was calculated in days and need to be converted into weeks, months or years the following conversion factors need to be used:

1 week = 7 days
1 month = 30.4 days
1 year = 365.25 days

6.1.7 Pooling of Investigator Sites

The primary analysis will use data pooled across all investigative sites. The Regions (UK, US, Canada, New Zealand, Israel, Slovakia, etc.) and site differences may be explored in preliminary analyses depending on how many subjects randomized by each site/region. Preliminary exploratory analyses may be conducted to determine potential influence of treatment-by-investigative site/region interaction on the primary and key secondary efficacy endpoints by graphical visualization and tabulations of the data and where necessary, using statistical models incorporating treatment, site, and treatment-by-site interaction. A significance level of 0.10 will be used in any of the analyses in identifying potential treatment-by-site interactions. The exploratory results indicating non-significant interaction will be indicative that pooled data across sites/regions was free of the impact of any extreme investigative sites/regions. It is recognized that the power to detect an interaction will be limited due to some sites with limited enrollments.

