	 Change in dose or discontinuation of oral 5-aminosalicylic acid (5-ASA) compounds less than 4 weeks prior to baseline. 				
	 Change in dose or discontinuation of corticosteroids less than 2 weeks prior to baseline. 				
	 Change in dose or discontinuation of azathioprine, 6-mercaptopurine (6-MP) or methotrexate less than 8 weeks prior to baseline. 				
	 Change in dose or discontinuation of infliximab or adalimumab less than 14 weeks prior to baseline. 				
	 Treatment with vedolizumab less than 120 days prior to baseline or biological therapies (apart from infliximab or adalimumab) less than 60 days prior to baseline. 				
	Previous treatment with rifabutin and/or clofazimine.				
	 Oral or parenteral antibiotics in the 4 weeks prior to baseline (topical antibiotics are permitted). 				
	 Treatment with probiotics (excluding yogurt and yogurt-derived products) in the 4 weeks prior to baseline. 				
	Females who have a positive pregnancy test or are lactating.				
Number of Subjects:	Estimated total: 410 subjects, curtailed to 324 with Protocol Version 11.0, will be randomized into the study.				
Number of Sites:	The study will be conducted at up to 150 sites in the USA, Canada, Israel, Australia, New Zealand, Poland, Bulgaria, Czech Republic, Romania, Slovakia and Serbia.				
Study Design:	This study is a multicenter, Phase III, randomized, placebo-controlled, double-blind study designed to evaluate the efficacy and safety of RHB-104 compared to placebo to treat subjects with moderate to severe CD. RHB-104 consists of 3 antibiotics with activity against Mycobacterium avium subsp. paratuberculosis (MAP), a potential cause of CD. Subjects with active CD will be randomized at baseline in a 1:1 fashion to receive up to 52 weeks of RHB-104 or placebo. Randomization will be performed within strata defined by whether subjects use protocol permitted anti-TNF agents (yes or no). Subjects will remain on stable doses of their baseline CD treatment although steroids may be tapered after Week 8 at the discretion of the investigator.				

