6.1.9 Determination of Sample Size

The sample size justification is provided in the protocol and was based on the review of published literature in similar patient population (Sandborn et al., 2013). A total sample size of 410 subjects (205 per treatment arm) was computed to be sufficient with one stratification anti-TNF agent use (yes/no) to detect a minimum difference of 15 percentage points between RHB-104 treatment (36% Remission) and Placebo (21% Remission) with 90% Power at two-sided significance level, $\alpha=0.05$. The test statistic used for this analysis was a two-sided Cochran-Mantel-Haenszel (CMH) test controlling for the stratification variable (anti-TNF agents (yes/no) under the ITT principle. These calculations were made to allow for two sequential tests to be made using the O'Brien-Fleming spending function to determine the test boundaries. The interim analysis (first sequential test) will occur when 50% of the patients have their outcome data measured (i.e., reach 26 weeks of follow-up). The 2-sided alpha level for stopping the trial for efficacy at the interim analysis is 0.003. If this criterion is not met the trial will be continued and the final analysis (second sequential test) will be performed using a 2-sided alpha level of 0.049 for testing the primary outcome (Elashoff, 2007). In all analyses, subjects with missing 26 week assessments will be assumed to not be in a state of remission at 26 weeks.

It should be noted that the intervention effect used in the sample size derivation for the study is 15% improvement in 26 week remission success, however a clinically meaningful difference in this measure (26 week remission success proportion) is 9% (in absolute percent) based on clinical expert opinion. Therefore, any statistically significant difference between groups that has an observed percent difference of 9% or larger would indicate that treatment is effective.

Protocol Version 11.0 curtails the number of expected enrolled patients to 324 (162 per group). Final analysis of the data is to be carried out when approximately 324 patients have completed the Week 26 primary endpoint assessment. This sample size curtailment reflects the study's current accrual trends. The anticipated power will be at least 80% given the study design stage assumptions regarding the treatment groups primary efficacy endpoint (36% RHB-104 vs. 21% Placebo).

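### SAP 6.1.7 would read a non-significant treatment-by-site or treatment-by-region interaction as absence of extreme sites or regions, an inference the test cannot support

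*SAP*

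**What the plan says.** SAP 6.1.7 (Pooling of Investigator Sites) pools all sites for the primary analysis. It then allows an optional look at heterogeneity: "Preliminary exploratory analyses may be conducted to determine potential influence of treatment-by-investigative site/region interaction" on the primary and key secondary endpoints, by graphs and tabulations and, where necessary, by models with treatment, site and their interaction. The threshold is set: "A significance level of 0.10 will be used in any of the analyses in identifying potential treatment-by-site interactions". The reading of a null result is set too: "The exploratory results indicating non-significant interaction will be indicative that pooled data across sites/regions was free of the impact of any extreme investigative sites/regions". The section closes with a caveat: "It is recognized that the power to detect an interaction will be limited due to some sites with limited enrollments".

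The size of the trial comes from the protocol synopsis. The planned sample size was reduced: "Estimated total: 410 subjects, curtailed to 324 with Protocol Version 11.0, will be randomized into the study". For sites the synopsis gives a ceiling rather than a count: "The study will be conducted at up to 150 sites". It names 11 countries: "USA, Canada, Israel, Australia, New Zealand, Poland, Bulgaria, Czech Republic, Romania, Slovakia and Serbia". Randomisation is 1:1 within strata of anti-TNF use (synopsis, Study Design; SAP 4.3). Site is not named as a stratum.

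**The concern.** The sentence treats failure to reject as evidence that there is nothing to find. That would be defensible only if the test were likely to find an extreme site or region when one exists. The caveat that follows says the opposite, yet does not withdraw the inference. The two sentences cannot both guide the report.

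What is at stake is a claim in the study report that the result is consistent across sites and regions, made on the strength of a test that is weak for regions and close to uninformative for single sites. The SAP gives no minimum site size, no rule for combining small sites, and no named interaction test.

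**Working it through.** **Inputs from the documents.** N = 324 (162 per arm); up to 150 sites; 11 countries; remission 21% placebo and 36% RHB-104; interaction alpha 0.10.

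**The plan's own figure.** The documents give no interaction power, so the only figure to reproduce is the main-effect power. A two-proportion test of 36% versus 21% at two-sided 0.049 with 162 per arm has 85% power, or about 82% with continuity correction. This agrees with the stated minimum of 80%.

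**Site level: sparsity.**
- Mean subjects per site: 324/150 = 2.16. The number of sites that enrol is not given. Assuming 100 sites, 324/100 = 3.24; assuming 50, 324/50 = 6.48.
- A model with site, treatment and interaction at 150 sites has 150 + 1 + 149 = 300 parameters for 324 subjects.
- Simulated allocation, assuming equal expected site size, 150 sites and no balancing of arms within site: about 133 sites enrol anyone, 66 have both arms, 13 have at least two subjects per arm, and 40 have both arms and mixed outcomes.

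**Site level: behaviour of the test.** Simulated under a uniform 15-point effect, nominal level 0.10, N = 324:
- A likelihood-ratio interaction test rejected in 33% to 100% of trials, depending on the number of sites and on how degrees of freedom are counted for sparse sites.
- A score test of the Breslow-Day type rejected about 88% of the time at 150 sites, 73% at 100 and 32% at 50.

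So the nominal 0.10 level does not hold. With the score test recalibrated to a true 10% size, the chance of detecting one aberrant site is:

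| Sites (assumed) | One site at −15 points | One site at +60 points | One site where all treated remit |
|---|---|---|---|
| 150 | 9.9% | 11.6% | 12.3% |
| 100 | 11.1% | 11.7% | 13.4% |
| 50 | 11.6% | 12.6% | 16.5% |

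These figures lie close to the 10% rejection rate when no site is extreme.

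**Region level.** Assume a share *w* of subjects is in a region with zero effect, the trial average is 15 points, placebo remission is 21% everywhere, and arms are balanced within region. The effect elsewhere is then d = 0.15/(1 − w). The test statistic is the difference of the two risk differences, with

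SE² = 2(0.21)(0.79)/(162w) + [(0.21)(0.79) + (0.21 + d)(0.79 − d)]/(162(1 − w))

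and power = Φ(d/SE − 1.645) + Φ(−d/SE − 1.645).

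| w | d | SE | d/SE | Power | Missed |
|---|---|---|---|---|---|
| 10% | 0.167 | 0.152 | 1.09 | 29% | 71% |
| 20% | 0.188 | 0.116 | 1.62 | 49% | 51% |
| 30% | 0.214 | 0.102 | 2.10 | 67% | 33% |

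Other simulated layouts show the range. With 11 equal countries (324/11 = 29.5 each), the calibrated score test detects one country with a reversed effect (−15 points) about 27% of the time, one at +60 points about 36%, and one where every treated subject remits about 78%. With four equal regions, one reversed region is detected about 79% of the time.

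**The case against.** The strongest reply is that nothing depends on this test. The analysis is optional, models are fitted only where necessary, the inference is worded as indicative, and limited power is conceded at once. Pooling is fixed whatever the result, and SAP 6.3.1 stratifies the primary CMH test by anti-TNF use only. Region is already a listed subgroup in SAP 6.1.3. All of this stands, and it limits the point to interpretation. It does not rescue the sentence, because conceding low power while keeping the conclusion leaves the conclusion unsupported.

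A second reply is that the zero-effect region is a mild case. Removing it would move the estimate from 15 to 16.7, 18.75 or 21.4 points, so the region dilutes the benefit rather than creating it. That is fair. The miss rates of 71%, 51% and 33% measure undetected heterogeneity; they do not say how often the pooled result would mislead.

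Three stronger readings are tempting and are not supported:
- **That non-significance is to be expected at site level whatever the truth.** The SAP names no test, and the likelihood-ratio and score tests examined tend to reject too often when uncorrected. The test is unreliable in both directions.
- **That there are two subjects per site.** That is an average at a ceiling. No site count or distribution is given, and the SAP's own caveat suggests uneven enrolment.
- **That regions are as sparse as sites.** Countries average about 29 subjects, and four equal regions would give fair power against a reversed effect.

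**Conclusion.** The point holds as a defect of interpretation. A non-significant interaction at 0.10 does not show that the pooled data are free of extreme sites or regions. For one extreme site, calibrated power is about 10% to 17% across 50 to 150 assumed sites. For a region with 10% to 30% of subjects and no effect, power is about 29% to 67%.

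These figures rest on assumed site counts, equal expected site sizes, the design-stage remission rates and the chosen scenarios. Few, large regions would do better. A reader might infer that the primary result or the type I error is at risk; the documents do not support that, since neither depends on this test. The consequence is confined to an unsupported consistency statement, so the importance is low.

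**What to change.** In SAP 6.1.7:
1. Replace the inference with a statement that a non-significant interaction does not exclude heterogeneity between sites or regions.
2. Do not fit the treatment-by-site model at individual-site level.
3. Base any consistency statement on region-specific risk differences with 95% confidence intervals, using the region subgroup of SAP 6.1.3 and defining the regions before unblinding.
4. Repeat the primary CMH analysis leaving out each country, and each of the largest sites, in turn.

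The leave-one-out table is one reasonable way to address the impact of an extreme site directly; the necessary correction is the wording in item 1. The cost is SAP text and one short exploratory table. It needs no new data and no change to the primary analysis.
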